9.2.2 Serious adverse events (SAEs)

A serious adverse event is any untoward medical occurrence or effect that

- results in death;
- is life threatening (at the time of the event);
- requires hospitalisation or prolongation of existing inpatients' hospitalisation;
- results in persistent or significant disability or incapacity;
- is a congenital anomaly or birth defect; or
- any other important medical event that did not result in any of the outcomes listed above due to medical or surgical intervention but could have been based upon appropriate judgement by the investigator.

An elective hospital admission will not be considered as a serious adverse event.

The sponsor will report the SAEs through the web portal *ToetsingOnline* to the accredited METC that approved the protocol, within 7 days of first knowledge for SAEs that result in death or are life threatening followed by a period of maximum of 8 days to complete the initial preliminary report.

Because this study is without any risks for the patient, we will report all SAEs once per year.

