9. SAFETY REPORTING

9.1 Temporary halt for reasons of subject safety

In accordance to section 10, subsection 4, of the WMO, the sponsor will suspend the study if there is sufficient ground that continuation of the study will jeopardise subject health or safety. The sponsor will notify the accredited METC without undue delay of a temporary halt including the reason for such an action. The study will be suspended pending a further positive decision by the accredited METC. The investigator will take care that all subjects are kept informed.

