9.3 Annual safety report

Not applicable.

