9.4 Follow-up of adverse events

All AEs will be followed until they have abated, or until a stable situation has been reached. Depending on the event, follow up may require additional tests or medical procedures as indicated, and/or referral to the general physician or a medical specialist. SAEs need to be reported until end of study within the Netherlands, as defined in the protocol

9.5 [Data Safety Monitoring Board (DSMB) / Safety Committee]

Not applicable.

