12.4 Annual progress report

The sponsor/investigator will submit a summary of the progress of the trial to the accredited METC once a year. Information will be provided on the date of inclusion of the first subject, numbers of subjects included and numbers of subjects that have completed

the trial, serious adverse events/ serious adverse reactions, other problems, and amendments.

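### Section 9.2.2 gives two unreconciled reporting timelines for fatal and life-threatening SAEs: 7 days (plus up to 8 to complete), and once a year for every SAE

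*Combined protocol and SAP*

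**What the plan says.** Section 9.2.2 defines an SAE by six criteria, of which death and threat to life are the first two. It then has the sponsor report SAEs to the approving METC through the web portal, "within 7 days of first knowledge for SAEs that result in death or are life threatening followed by a period of maximum of 8 days"; the further days are for finishing the preliminary report. A separate paragraph follows at once: "Because this study is without any risks for the patient, we will report all SAEs once per year".

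Four other places bear on SAE reporting:

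- Section 9.1: "the sponsor will suspend the study if there is sufficient ground that continuation of the study will jeopardise subject health or safety", with notice of the halt to the METC.
- Section 9.3 marks the annual safety report as not applicable.
- Section 9.4: "SAEs need to be reported until end of study within the Netherlands, as defined in the protocol".
- Section 12.4: "The sponsor/investigator will submit a summary of the progress of the trial to the accredited METC once a year". The listed content includes "serious adverse events/ serious adverse reactions, other problems, and amendments".

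Section 9.5 provides for no DSMB or safety committee. Section 3 plans 12 months in all, 6 for inclusion and 6 for follow-up.

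On risk, sections 9.2.2, 11.5 and 13.2 treat participation as risk-free. Section 11.4 describes patients' false sense of safety as a major potential risk. Section 6.4 names that same risk and a second one, alarm caused by a wrong AF detection.

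**The concern.** A death during follow-up meets the SAE definition, so both sentences of 9.2.2 apply to it. One asks for a report within days and the other for a report once a year. The second opens with a reason for lighter reporting and carries no word such as other, remaining or additional to limit it. Someone handling the event could follow either sentence and believe that they were complying with the protocol.

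What is at stake is how soon the METC hears of the gravest events. With no DSMB, the METC is the only body outside the study team that the documents name as receiving SAE reports. The reason given for the yearly rule is also one that sections 6.4 and 11.4 do not bear out.

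**Working it through.** The plan states no statistical figure to reproduce here. The check sets the passages side by side and subtracts the two time limits.

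1. **Do both sentences cover the same events?** The first is limited to fatal and life-threatening SAEs. The second covers all SAEs, and the definition in the same section places these two categories among them. They therefore fall under both. For the other four criteria no time limit is given apart from the yearly one, so there is no conflict for them.

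2. **Does another section settle it?**
   - 9.1 brings the METC in only when the sponsor finds ground to suspend the study. A death that does not lead to a halt would not reach it by that route.
   - 9.3 removes one possible form of yearly report and sets no time limit.
   - 9.4 says until when SAEs are reported, not how quickly.
   - 12.4 places SAEs in a yearly METC report, but does not say whether this adds to the 7-day report or replaces it.

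   None of them decides which sentence of 9.2.2 governs.

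3. **Who receives the yearly report?** The sentence does not say. The METC is inferred from the paragraph before it and from 12.4.

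4. **How far apart are the timelines?** Inputs: 7 days and 8 days (9.2.2), and one year (9.2.2), taken as 365 days. All are counted from first knowledge.
   - 7-day sentence: first report by day 7; completed report by day 7 + 8 = 15.
   - Yearly sentence alone: up to about day 365, because the yearly date is not given.
   - Largest difference, first report: 365 − 7 = 358 days.
   - Largest difference, completed report: 365 − 15 = 350 days.

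   These are upper bounds. They need an event that becomes known just after a yearly reporting date or, with a single report at month 12, at the very start of the study. An event known m months into the study would wait 12 − m months for that report. At m = 6, for example, the wait is 12 − 6 = 6 months.

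5. **How many yearly reports would there be?** Planned duration is 6 + 6 = 12 months. At one report per 12 months, 12 / 12 = 1 report could cover the whole study.

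6. **Does the stated reason hold?** 9.2.2 rests the yearly rule on the absence of any risk. 11.4 names a risk that it calls major, which contradicts this directly. 6.4 names two risks, the first of them the same as in 11.4, so there are two distinct named risks. The milder descriptions in 6.4 (very limited) and 12.2 (negligible) differ from risk-free only in degree.

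**The case against.** The strongest reply is that this is an ambiguity and not a proven contradiction. Under the usual preference for the specific rule over the general one, each sentence has a job: the first sets the limit for fatal and life-threatening SAEs, and the second supplies the limit that the other categories lack. A cumulative reading is also available. The yearly sentence does not say that SAEs are reported only yearly, and 12.4 puts SAEs in a yearly METC report without displacing the 7-day one. Both readings are workable, and this stands. But the text states neither, and a clause giving a reason for lighter reporting fits poorly with a listing that is merely additional.

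A second reply is that oversight is not as thin as the absence of a DSMB suggests. Section 12.2 proposes independent nurses as monitors, section 9.2.1 has adverse events recorded, and section 9.1 keeps the duty to suspend. This is fair. However, the documents do not say that the monitors receive SAE reports, and neither recording an event nor the duty to suspend fixes when the METC hears of a death.

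A third reply is that the missing name for the yearly report is no real gap, since 12.4 already provides a suitable one. That is right, and the fix uses it.

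**Conclusion.** The point holds as an unreconciled pair of timelines, confined to fatal and life-threatening SAEs. If the yearly sentence were followed alone, METC notice could come as late as the yearly report: at most about 365 days after first knowledge, against 7 days for the first report and 15 for the completed one. This assumes that the yearly report goes to the METC, which is inferred, and that the yearly sentence is taken to override the other, which the text does not establish.

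A reader might infer more than the documents support:

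- That the plan abolishes 7-day reporting. It does not; that sentence is current text.
- That 358 or 350 days is a typical delay. Each is an upper bound.
- That some number of reports would be late. The documents give no expected number of such events among the 55 patients.
- That the results are affected. The primary parameter and the analysis do not depend on this.

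The sponsor should correct it, because the remedy is small and it protects timely oversight.

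**What to change.** In 9.2.2, merge the two sentences into one rule with explicit scope. The yearly listing of SAEs is carried in the annual progress report of 12.4. It does not replace the 7-day report, with up to 8 further days to complete, for fatal and life-threatening SAEs. It is the sole timeline only for the other SAE categories. Name the METC as recipient of the yearly listing. In the same paragraph, drop the no-risk justification or bring it into line with 6.4 and 11.4.

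This costs wording only. It adds no individual report beyond those the 7-day sentence already requires, and it does not touch design, sample size or analysis.

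The no-risk premise in 11.5 and 13.2 should be flagged to the sponsor as a separate inconsistency. It is not a wording-only change: in 11.5 the premise is the ground for requesting dispensation from insurance, and in 13.2 it is the reason for omitting 13.1. Correcting it may mean revisiting both.

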9.2.3 Suspected unexpected serious adverse reactions (SUSARs)

Not applicable.

9.3 Annual safety report

Not applicable.

9.4 Follow-up of adverse events

All AEs will be followed until they have abated, or until a stable situation has been reached. Depending on the event, follow up may require additional tests or medical procedures as indicated, and/or referral to the general physician or a medical specialist. SAEs need to be reported until end of study within the Netherlands, as defined in the protocol

9.5 [Data Safety Monitoring Board (DSMB) / Safety Committee]

Not applicable.

10. STATISTICAL ANALYSIS

10.1 Primary study parameter(s)

We will use descriptive statistics to assess blood pressure management, patient engagement and user-based evaluation of the eHealth infrastructure. We will analyze their self-measurement frequency of blood pressure, heart rhythm, weight, and activity using the mean measurements per week. The dropout rate will be described and the change in blood pressure in mmHg. This will be used as a basis for sample size calculation for future trials.

Moreover, we will use descriptive statistics to assess the clinical characteristics of our sample population.

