Main study parameters/endpoints: The primary objective of this study is the gathering of data on blood pressure management as a basis for power analysis in future trials. The secondary objectives will be gathering and evaluating data on heart rhythm, weight and activity of patients, evaluating the technical- and workflow implementation for healthcare professionals, evaluating the self-management and user-experience of patients, assessing the patient adherence to the self-measurements and pharmacotherapeutic prophylactic therapy, and finally evaluating the technical feasibility for all stakeholders.

Nature and extent of the burden and risks associated with participation, benefit and group relatedness: Patients are asked to measure weight, blood pressure and heart rhythm on a weekly basis, which takes approximately 5-10 minutes. All devices used by patients for personal management in this study are non-invasive, easy-to-use, CE marked and electrically safe within their intended use. Using the devices comes with very limited risks. This study has several potential benefits for patients. First, patients can measure their own blood pressure, heart rhythm and weight, which can give them more insight in their own health and may spark a healthier lifestyle (the so-called 'patient empowerment'). Furthermore, these data give the GP or GP nurse more insight in the health status of patients, potentially leading to better cardiovascular risk management and hypertension control. Finally, the regular ECG measurements might help in detecting occult AF in patients at risk for AF.

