8.1.2 Secondary study parameters/endpoints

The secondary objectives of this study are:

- Gathering data on self-measured heart rhythm from the Withings Move ECG as an indicator of atrial fibrillation, weight and activity of patients using the Stroke Box, and performing a quality assessment of the collected data as assessed by regularity of assessments and frequency of occurrence of measurement error.
- The potential change in self-management of the patients due to the Stroke Box as measured through changes in lifestyle. This will be measured using changes in results from questionnaires on physical activity and healthy lifestyle intentions taken at the start and at the end of the study and the development of weight of the patient.

For the evaluation of physical activity we will adapt the Short Questionnaire to Assess Health enhancing physical activity questionnaire (SQUASH)²⁰, for the evaluation of healthy lifestyle intentions we will use the Healthy Lifestyle Intentions (HLI) questionnaire.

The evaluation of the self-management of the patient will be assessed by the Reach Efficacy Adoption Implementation Maintenance (RE-AIM) model with a mixed model evaluation based on the normalization process theory.²¹⁻²³

- Assessment of the patient adherence to the self-measurements and pharmacotherapeutic prophylactic therapy, using the Partners In Healthcare (PIH) questionnaire which measures how the patient manages his/her own disease. At the end of the study a comparison will be made between the group of patients who used the IkOefenZelf platform and those who did not.
- The technical implementation and patient adherence to the self-measurements by analysing how often they performed the measurements, if they experienced any problems as measured through the questions they asked during the study, and how they experienced the overall implementation as measured through the mHealth App Usability Questionnaire (MAUQ)²⁴ at the end of the study.
- User based evaluation of the technical – and workflow implementation for the GPs using the Stroke Box as evaluated with the Acceptability of Intervention Measure (AIM), Intervention Appropriateness Measure (IAM), and Feasibility of Intervention Measure (FIM)²⁵ questionnaires for healthcare professionals.

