8.3 Study procedures

For the small prospective cohort for the pilot, patients who are admitted for an ischemic or hemorrhagic stroke in the LUMC will be included in the day or days before dehospitalization and after post-stroke stabilization. After inclusion we will personally contact the GP of the patient to also ask their willingness to collaborate in the pilot. After agreement of their GP, the included patients will receive the Stroke Box with all devices listed under section 6 of this protocol. Patients will be instructed on usage of the devices by a neurology PhD student. Furthermore, for each device a detailed user guide is available on <https://hartlongcentrum.nl/informatie-voor-patienten/the-box/handleidingen/>.

If extra help is necessary, patients will have an e-consult in which a patient does not have to go to the hospital. Instead, he or she will talk with a specialist from the Box-helpdesk who will be able to guide the patient through the self-measurements and provide technical assistance where necessary.

Patients will be asked to measure their weight and blood pressure once a week where they are recommended to do this on the same day and time every week. Additionally, they will be asked to keep track of their activity data (i.e. steps) on a regular basis, which can be monitored continuously by wearing the smartwatch. All

data will be automatically transferred to the LUMC. In order to code the data, patients will receive an anonymous email address, as described earlier in this protocol. Data will be stored on LUMC-owned servers.

The patient's blood pressure measurements and lifestyle data (measured weight and activity) is accessible for the GP through Medical Dashboard. For GPs who do not yet work with Medical Dashboard, the patient will be asked to show his measurements to the GP in the following way during the regular visits. The patient can either show his measurements in the app or make a printout of the data to be shown to the GP or GP nurse.

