When the patient records abnormal measurements indicating a high or rapid increase in blood pressure, they are instructed to not immediately contact a physician. This, in order to reduce the amount of (unnecessary) additional consults with the GP. Specifically, the patient is instructed to only contact their GP if they record a systolic blood pressure >140 mmHg for three days in a row or take up immediate contact if they record a systolic blood pressure >180 mmHg which is cause for immediate adjustment of the hypertension medication according to the NHG guidelines.

In addition to the standard care where patients receive a 48-hour Holter, patients who are suspected to have atrial fibrillation because of e.g. a cryptogenic stroke will be asked to also perform home measurements of their heart rhythm on a daily basis. They are recommended to do this on the same day and time every day. They will be very clearly instructed that their ECG measurements are not monitored regularly and that they should contact 112 in case of emergency.

After a measurement the Withings Move ECG performs a standard analysis resulting in either "normal", "inconclusive" or "atrial fibrillation". If their ECG smartwatch shows "atrial fibrillation" they are instructed to contact a dedicated nurse specialist who will check the measurements and refer them to the cardiology outpatient clinic if necessary. If the result is "inconclusive", the patient is asked to repeat the measurement the next day. When the repeated measurement shows "inconclusive" again or when the measurement shows a warning for potential AF, they are instructed to also contact the dedicated nurse specialist who will contact the patient for further follow-up if necessary. It should be noted that a clinical diagnosis will never be based on the self-measurements. Instead they serve as an early screening tool leading to patients with potential AF to be invited to the cardiology outpatient clinic to receive a diagnosis via the standard Holter measurement.

All ECG data are collected after the study and re-inspected by a PhD researcher of the LUMC for AF and in case of doubt checked again by an experienced cardiologist. In case of suspected AF, the patient is invited to the cardiology outpatient clinic. As 87% of stroke patients have ischemic strokes¹⁶ and about a

third of those have cryptogenic strokes, we expect to find cryptogenic strokes in about 29% of the LUMC stroke population.¹⁷

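### Section 10.1 reports self-measurement frequency only as an uncapped weekly mean with no stated denominator, so extra blood pressure readings can offset missed weeks

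*Combined protocol and SAP*

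**What the plan says.** Adherence to self-measurement is a secondary objective (section 2). Section 8.1.2 will assess "patient adherence to the self-measurements by analysing how often they performed the measurements". The analysis in section 10.1 is descriptive, and the only frequency statistic it names is this: "We will analyze their self-measurement frequency of blood pressure, heart rhythm, weight, and activity using the mean measurements per week". It does not say whether the mean is taken per patient, per study week or over everything together. Nor does it say whether weeks after a patient stops count in the denominator. The next sentence adds that a dropout rate will be described, without defining dropout.

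The requested schedule in section 8.3 differs by device:

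- **Blood pressure and weight:** "Patients will be asked to measure their weight and blood pressure once a week".
- **Heart rhythm:** patients with suspected atrial fibrillation are "asked to also perform home measurements of their heart rhythm on a daily basis". The Summary, in its paragraph on burden and risks, says instead: "Patients are asked to measure weight, blood pressure and heart rhythm on a weekly basis".
- **Activity:** tracked continuously by the watch, with no weekly count requested.

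Two instructions in section 8.3 bear on the count. Short of a single reading above 180 mmHg, patients should "only contact their GP if they record a systolic blood pressure >140 mmHg for three days in a row". After an inconclusive ECG, "the patient is asked to repeat the measurement the next day".

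**The concern.** When the request is one reading a week, the adherence question is in how many weeks a reading was taken. An uncapped average answers a different question, because a second reading in one week cancels an empty week elsewhere.

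For blood pressure the surplus need not come only from keen patients. A weekly schedule cannot produce high values on three consecutive days, so the contact rule can be met only through readings outside the schedule. Section 4.2 admits only patients with systolic pressure above 140 mmHg in hospital, so the rule is likely to come into play. The count would then rise with poor blood pressure control, and blood pressure is the main study parameter (section 8.1.1).

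Section 10.1 says its results will be a basis for the sample size of future trials. If adherence is overstated, the next trial may allow for too little missing blood pressure data. Section 1 itself expects that disability may reduce uptake of self-monitoring in this population.

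**Working it through.** The documents state no adherence figure, so there is none to reproduce.

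**Inputs from the documents:** 55 patients (section 4.4); six months of follow-up, taken as 26 weeks (section 3); one blood pressure reading requested per week (section 8.3). This gives 55 × 26 = 1,430 scheduled patient-weeks.

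**Assumptions, not in the documents:** when patients stop, and how many surplus readings the others take.

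1. **One patient.** Two readings a week for 13 weeks, then none: mean = 2 × 13 / 26 = 1.0 per week; weeks covered = 13 / 26 = 50%.

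2. **Cohort, patients stopping halfway.** Suppose 27 patients read once a week and stop after week 13, and 28 continue at 1.5 per week.
   - Readings: 27 × 13 + 28 × 26 × 1.5 = 351 + 1,092 = 1,443. Mean = 1,443 / 1,430 = 1.01 per week.
   - Weeks covered: (351 + 28 × 26) / 1,430 = 1,079 / 1,430 = 75.5%.
   - Still measuring at week 26: 28 / 55 = 50.9%.

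3. **Cohort, patients stopping early.** Suppose 40% read once a week and stop after week 4, and 60% continue at 1.5 to 2.0 per week.
   - Mean = 0.4 × 4/26 + 0.6 × 1.5 = 0.96, up to 0.4 × 4/26 + 0.6 × 2.0 = 1.26.
   - Weeks covered = 0.4 × 4/26 + 0.6 = 66%.

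4. **Break-even.** If a completed three-day run occurs in a share f of active weeks and adds two readings, active patients average r = 1 + 2f. If a share s of patients stops at the start, the overall mean is (1 − s) × r, which equals 1 when s = 1 − 1/r.

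| f (assumed) | r | s that still gives a mean of 1.0 | whole patients of 55 |
|---|---|---|---|
| 0 | 1.0 | 0% | 0 |
| 0.10 | 1.2 | 16.7% | 9 |
| 0.25 | 1.5 | 33.3% | 18 |
| 0.50 | 2.0 | 50% | 27 |

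5. **No surplus.** Repeat step 2 with all 28 continuing patients at one reading a week: (351 + 728) / 1,430 = 0.755, the same as the share of weeks covered. With all patients and weeks in the denominator, masking therefore needs surplus readings.

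6. **Denominator limited to active weeks.** At one reading per active week, the mean stays at 1.0 however many patients stop. Section 10.1 does not rule this out.

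7. **ECG.** Under the daily request in section 8.3, a next-day repeat coincides with a reading already due and adds nothing. Under the weekly wording of the Summary it adds one. The value that represents full adherence is also unclear. It is 1 per week if everyone measures weekly. If the daily group is the 29% that section 4.4 expects to have cryptogenic stroke (an assumption), the mean over all patients is 7 × 0.29 = 2.03 with no ECGs from the others, or 7 × 0.29 + 0.71 = 2.74 with weekly ECGs from the others.

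8. **Weight and activity.** No repeat rule exists for weight, so a surplus there would come only from patients' own habits. For a continuously recorded measure, a count per week has no clear meaning.

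**The case against.** The strongest reply is that section 10.1 promises descriptive statistics in general, and that its wording can be read more kindly. As a mean per patient, then described across patients, step 2 would show stoppers at 0.5 and continuers at 1.5. As a mean for each study week, it would fall from (27 + 28 × 1.5) / 55 = 1.25 in weeks 1 to 13 to 28 × 1.5 / 55 = 0.76 in weeks 14 to 26. This stands in part: only a single pooled figure hides that example completely. But the plan does not choose between the readings. The patient in step 1 still scores 1.0 on the per-patient version, and 0.76 still overstates the 50.9% who are measuring.

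A second reply is that the dropout rate will be reported and would naturally inform a missing-data allowance. That softens the point. However, section 8.4 speaks of leaving the study, and a patient can stop measuring without leaving. Section 8.1.2 also mentions regularity, but attaches it to heart rhythm, weight and activity, and section 10 gives no statistic for it.

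Third, the extra blood pressure readings are implied, since the rule says when to contact the GP and does not order repeats. That is correct, and their frequency is unknown.

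A reader might also infer three stronger claims that the documents do not support:

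- **That the mean does not track adherence.** It does rise with adherence; for blood pressure it is mixed with blood pressure control.
- **That a go/no-go decision would be misled.** The documents contain no progression criterion or adherence threshold. The stated use is sample size planning.
- **That ECG repeats inflate the count in general.** They do so only under the weekly wording.

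**Conclusion.** The point holds for blood pressure, the main parameter, and more weakly for weight. The planned mean can equal the requested one reading per week while a substantial share of weeks has no reading: 50% for the single patient in step 1, and about a quarter to a third in the cohort illustrations in steps 2 and 3. Those sizes rest on assumed stopping patterns and surplus readings, and on pooling over all patients and weeks. Without surplus and with a full denominator, there is no distortion. The defect is that the plan neither caps the count nor fixes the denominator, while its own contact rule implies surplus readings in a cohort selected for high systolic pressure. This should be corrected. It does not undermine the pilot, because the readings allow a better summary.

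**What to change.** In section 10.1:

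- For blood pressure and for weight, report per patient the proportion of the scheduled weeks (about 26) with at least one valid reading, over all enrolled patients. Count weeks after a patient stops as not covered, and show withdrawals separately.
- For patients asked for daily ECGs, use the proportion of scheduled days with an ECG. For activity, use days on which the watch was worn.
- Give the median and interquartile range, and a week-by-week curve of the share still measuring. A cut-off such as 80% of weeks is optional; nothing in the documents calls for one.
- Define dropout so that it includes stopping measurement without withdrawing.
- Keep mean readings per week as a secondary description, with its denominator stated.

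The Summary and section 8.3 must be reconciled on ECG frequency, because the ECG denominator depends on it. Which schedule applies is for the sponsor to settle.

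The cost is a wording change. Sections 5.1 and 8.3 already provide for automatic transfer of the readings, so no new data collection is needed. The downside is that reported adherence may look less favourable.
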